8.2.4. Pre-vaccination body temperature

The oral or axillary or rectal body temperature of each subject needs to be measured prior to any study vaccine administration. If the subject has fever (fever is defined as temperature $\geq 38.0^{\circ}\text{C}/100.4^{\circ}\text{F}$ regardless of the location of measurement) on the day of vaccination, the vaccination visit will be rescheduled within the allowed interval for this visit (see Section 6.3).

8.3. Safety Assessments

The investigator and any designees are responsible for detecting, documenting, and reporting events that meet the definition of an AE or SAE. The investigator and any designees remain responsible for following up AEs that are serious, considered related to the study treatment or the study, or that caused the subject to discontinue the study.

8.3.1. Safety definitions

Please refer to Section 12.3 for safety definitions.

8.3.2. Time period and frequency for collecting adverse event and serious adverse event information

An overview of the protocol-required reporting periods for AEs and SAEs is given in Table 7. Refer to the Section 12.3.6.1 for details on the time period for recording safety information.

Table 7 Reporting periods for collecting safety information

Study activity	Pre-V*	V1 Dose 1	7 days Post- V1	30 days Post- V1	V2 Dose 2	7 days Post- V2	30 days Post- V2	V3 (30 days after the last dose)	ESFU (Study conclusion)
		Day 1			Month 1-2			Month 2-4	Month 7-8
Solicited general AEs									
Unsolicited AEs									
AEs/SAEs leading to withdrawal									
SAEs									
SAEs related to study participation or GSK concurrent medication/vaccine									

* Consent obtained. Pre-V: pre-vaccination; V = Visit.

CONFIDENTIAL208236 (ROTA-096)
Protocol Amendment 2

All SAEs will be recorded and reported via Expedited Adverse Event Reporting Form to the sponsor or designee immediately and under no circumstance should this exceed 24 hours after the investigator became aware of it, as indicated in section [12.3](#) (Appendix 3). The investigator will submit any updated SAE data to the sponsor within 24 hours of it being available.

A post-study AE/SAE is defined as any event that occurs outside of the AE/SAE reporting period defined in [Table 7](#). Investigators are not obligated to actively seek AEs or SAEs in former study subjects. However, if the investigator learns of any SAE, including a death, at any time after a subject has been discharged from the study, and he/she considers the event to be reasonably related to the study vaccines, the investigator will promptly notify the study contact for reporting SAEs.

8.3.3. Method of detecting AEs and SAEs

The method of recording, evaluating, and assessing intensity, causality and outcome of AEs and SAEs and the procedures for completing and transmitting SAE reports are provided in Section [12.3.6](#).

Refer to Section 8.4 for measures for safety follow-up that may be implemented during special circumstances (Amended 30 March 2020).

Care will be taken not to introduce bias when detecting AE and/or SAE. Open-ended and non-leading verbal questioning of the subject's parent(s)/LAR(s) is the preferred method to inquire about AE occurrence.

8.3.4. Reporting of serious adverse events

Table 8 Timeframes for submitting serious adverse event reports to GSK

Type of event	Initial reports		Follow-up of relevant information on a previous report	
	Time-frame	Documents	Time-frame	Documents
SAEs	24 hours*‡	electronic Expedited Adverse Events Report	24 hours*	electronic Expedited Adverse Events Report

* Time-frame allowed after receipt or awareness of the information.

† The investigator will be required to confirm review of the SAE causality by ticking the 'reviewed' box in the electronic Expedited Adverse Events Report within 72 hours of submission of the SAE.

CONFIDENTIAL208236 (ROTA-096)
Protocol Amendment 2**8.3.4.1. Contact information for reporting of serious adverse events****Table 9 Contact information for reporting of serious adverse events**

Study contact for questions regarding SAEs
Refer to the local study contact information document
Back-up study contact for reporting SAEs
24/24 hour and 7/7-day availability:
GSK Clinical Safety & Pharmacovigilance
Outside US & Canada sites:
Fax: PPD [REDACTED] or PPD [REDACTED]
Email address: PPD [REDACTED]
US sites only:
Fax: PPD [REDACTED]
Canada sites only:
Fax: PPD [REDACTED]

8.3.4.2. Regulatory reporting requirements for serious adverse events

Prompt notification of an SAE by the investigator to the sponsor is essential for meeting legal obligations and ethical responsibilities for the safety of subjects and the safety of a study treatment under clinical investigation.

The sponsor has a legal responsibility to notify both the local regulatory authority and other regulatory agencies about the safety of a study treatment under clinical investigation. The sponsor will comply with country-specific regulatory requirements relating to safety reporting to the regulatory authority, Institutional Review Boards (IRB)/Independent Ethics Committees (IEC), and investigators.

Investigator safety reports must be prepared for SUSAR according to local regulatory requirements and sponsor policy and forwarded to investigators as necessary.

An investigator who receives an investigator safety report describing an SAE or other specific safety information (e.g. summary or listing of SAEs) from the sponsor will review and then file it along with the IB and will notify the IRB/IEC, if appropriate according to local requirements.

8.3.5. Follow-up of adverse events and serious adverse events

After the initial AE/SAE report, the investigator is required to proactively follow each subject at subsequent visits/contact. All SAEs, will be followed until the event is resolved, stabilized, otherwise explained, or the subject is lost to follow-up. Further information on follow-up procedures is given in Section 12.3.9.

CONFIDENTIAL208236 (ROTA-096)
Protocol Amendment 2**8.3.6. Treatment of adverse events**

Treatment of any AE is at the sole discretion of the investigator and according to current good medical practice. Any medication administered for the treatment of an SAE should be recorded in Expedited Adverse Event Report of the subject's eCRF (refer to Section 7.5).

8.3.7. Subject card

Study subjects' parent(s)/LAR(s) must be provided with the address and telephone number of the main contact for information about the clinical study.

The investigator (or designate) must, therefore, provide a "subject card" to each subject's parent(s)/LAR(s). In an emergency situation, this card serves to inform the responsible attending physician that the subject is in a clinical study and that relevant information may be obtained by contacting the investigator.

Subjects' parent(s)/LAR(s) must be instructed to keep subject cards in their possession at all times during the study duration.

8.4. Study procedures during special circumstances (Amended 30 March 2020)

During special circumstances (e.g., COVID-19 pandemic), the specific guidance from local public health and other competent authorities regarding the protection of individuals' welfare must be applied.

For the duration of such special circumstances, the following measures may be implemented for enrolled participants:

- *Safety follow-up may be made by a telephone call, other means of virtual contact or home visit, if appropriate.*
- *Diary cards may be transmitted from and to the site by electronic means and/or conventional mail.*
- *If despite best efforts it is not possible to send diary cards to the site within the visit window as defined in the protocol (see Table 2), the diary cards should be returned to site before study end (the last ESFU contact).*
- *If despite best efforts it is not possible to administer the 2nd dose of study vaccine as defined in the protocol (see Table 2), a maximum age of 24 weeks may be used.*

CONFIDENTIAL208236 (ROTA-096)
Protocol Amendment 2

9. DISCONTINUATION CRITERIA

9.1. Discontinuation from the study

From an analysis perspective, a ‘withdrawal’ from the study refers to any subject who was not available for the concluding contact foreseen in the protocol.

All data collected until the date of withdrawal/last contact of the subject will be used for the analysis.

A subject is considered a ‘withdrawal’ from the study when no study procedure has occurred, no follow-up has been performed and no further information has been collected for this subject from the date of withdrawal/last contact.

Investigators will make an attempt to contact those subjects who do not return for scheduled visits or follow-up.

Primary reason for study withdrawal will be documented in the eCRF. The investigator will document whether the decision to withdraw a subject from the study was made by the subject’s parent(s)/LAR(s), or by the investigator, as well as which of the following possible reasons was responsible for withdrawal:

- AEs requiring expedited reporting
- Unsolicited non-serious AE
- Solicited AE
- Protocol deviation
- Withdrawal by subject, not due to an AE*
- Migrated/Moved from the study area
- Lost to follow-up
- Sponsor study termination
- Other (specify)

*In case a subject is withdrawn from the study because the subject’s parent(s)/LAR(s) has withdrawn consent, the investigator will document the reason for withdrawal of consent, if specified by the subject’s parent(s)/LAR(s), in the eCRF.

Subjects who are withdrawn from the study because of SAEs/AEs must be clearly distinguished from subjects who are withdrawn for other reasons. Investigators will follow subjects who are withdrawn from the study as result of an SAE/AE until resolution of the event (see Section [12.3.9](#)).

CONFIDENTIAL208236 (ROTA-096)
Protocol Amendment 2

9.2. Discontinuation of study vaccines

A ‘withdrawal’ from the study vaccines refers to any subject who does not receive the complete treatment, i.e. when no further planned dose is administered from the date of withdrawal. A subject withdrawn from the study vaccines may continue further study procedures (safety or immunogenicity) if planned in the study protocol, as deemed appropriate by the investigator.

Primary reason relative to premature discontinuation of the study vaccines will be documented on the Vaccine Administration screen of the eCRF. The investigator will document whether the decision to discontinue further vaccination/treatment was made by the subject’s parent(s)/LAR(s), or by the investigator, as well as which of the following possible reasons was responsible for withdrawal:

- AEs requiring expedited reporting
- Unsolicited non-serious AE
- Solicited AE
- Not willing to be vaccinated
- Other (specify).

9.3. Lost to follow-up

A subject will be considered lost to follow-up if subject’s parent(s)/LAR(s) repeatedly fails to return for scheduled visits and is unable to be contacted by the study site.

The following actions must be taken if a subject’s parent(s)/LAR(s) fails to return to the clinic for a required study visit:

- The site must attempt to contact the subject’s parent(s)/LAR(s) and reschedule the missed visit as soon as possible and counsel them on the importance of maintaining the assigned visit schedule and ascertain whether or not the subject’s parent(s)/LAR(s) wishes the subject to and/or should continue in the study.
- Before a subject is deemed lost to follow-up, the investigator or designee must make every effort to regain contact with the subject’s parent(s)/LAR(s) (where possible, 3 telephone calls and, if necessary, a certified letter to the parent’s/LAR’s last known mailing address or local equivalent methods). These contact attempts should be documented in the subject’s medical record.
- Should the subject’s parent(s)/LAR(s) continue to be unreachable, the subject will be considered to have withdrawn from the study with a primary reason of lost to follow-up.

CONFIDENTIAL

208236 (ROTA-096)
Protocol Amendment 2

10. STATISTICAL CONSIDERATIONS

10.1. Sample size determination

The target sample size is 1350 subjects (675 subjects per group).

Table 10 provides the 95% exact CI for different possible observed number of subjects with AEs for the study (675 subjects per group).

Table 10 Two-sided 95% exact confidence intervals for the true adverse event rate at different possible observed adverse event rates (675 subjects per group)

Subjects vaccinated	Observed number subjects reporting the adverse events	Observed percentage of subjects with the adverse events	95% exact confidence interval	
			Lower limit	Upper limit
675	0	0.0	0.0%	0.5%
	1	0.1	0.0%	0.7%
	10	1.5	0.7%	2.7%
	30	4.4	3.0%	6.2%
	50	7.4	5.5%	9.6%
	100	14.8	12.2%	17.7%

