routinely released for worldwide distribution. In order to keep the titer stable until administration during the study, the PCV-free study vaccine will be stored frozen.

Only in 2 countries, i.e. Canada and the US, an upper limit for the potency titer at release was required by the Regulatory Authorities and implemented for *ROTARIX* (lyophilized formulation in the US and liquid formulation in Canada). The upper limit was set at $6.5 \log_{10} \text{CCID}_{50}$ per dose. Following discussions with the FDA, it is being considered to increase the upper limit of the potency for the liquid formulation allowing acceptable range of potencies at release of the vaccine.

As part of the phase III studies, GSK plans to conduct study Rota-096, to evaluate the reactogenicity and safety of a PCV-free HRV liquid vaccine lot with a potency titer at release above $6.5 \log_{10} \text{CCID}_{50}$ per dose. The sample size of the study ensures completion of the total safety database size across the PCV-free development, as agreed with FDA.

A recent in-house pharmacovigilance analysis of the risk of intussusception (IS) after administration of the *ROTARIX* liquid vaccine (data lock point 15 January 2018) suggests no evidence of any association between the *ROTARIX* potency at release and the risk of IS. As no clear trend was observed in these data, FDA agreed that Rota-096 may proceed.

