6. ANALYSIS INTERPRETATION

All analyses are descriptive.

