10.1.4. Display of decimals**10.1.4.1. Percentages**

Percentages and their corresponding confidence limits will be displayed with 1 decimal

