10.1.5. Statistical methodology**10.1.5.1. Exact confidence intervals around proportions**

The exact confidence intervals around within-group proportions are derived using the method of Clopper and Pearson [[Clopper](#), 1934].

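### Two upper confidence limits in Protocol Table 10 are too low: 1/675 should read 0.8% (not 0.7%) and 30/675 should read 6.3% (not 6.2%)

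*Protocol*

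**What the plan says.** Protocol section 10.1 sets the size: "The target sample size is 1350 subjects (675 subjects per group"). It then introduces its one table of figures: "Table 10 provides the 95% exact CI for different possible observed number of subjects with AEs for the study (675 subjects per group"). Table 10 is titled "Two-sided 95% exact confidence intervals for the true adverse event rate at different possible observed adverse event rates (675 subjects per group"), with rows for 0, 1, 10, 30, 50 and 100 subjects reporting an event. The row for 1 subject (0.1%) gives limits of 0.0% and 0.7%. The row for 30 subjects (4.4%) gives 3.0% and 6.2%.

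The SAP fixes the rest of the calculation. Section 10.1.5.1 states: "The exact confidence intervals around within-group proportions are derived using the method of Clopper and Pearson". Section 10.1.4.1 states: "Percentages and their corresponding confidence limits will be displayed with 1 decimal".

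Section 10.1 contains no power calculation, margin or effect size, and SAP section 6 says "All analyses are descriptive". Protocol section 3.1 and the synopsis give one other reason for the size: "The sample size of the study ensures completion of the total safety database size across the PCV-free development, as agreed with FDA". No number accompanies it.

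**The concern.** In a descriptive safety study with no hypothesis test, the width of the confidence intervals is what a reader uses to judge whether the groups are large enough. Table 10 is the only place where the protocol puts figures on that. Two of its upper limits are lower than the stated method gives at the stated sample size, so the table promises slightly more than 675 subjects per group can deliver.

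The one-event row is the more consequential of the two. Protocol section 3.3.1 lists intussusception among the risks and section 7.7 calls its overall incidence rare, so a reader asking what a single case in one group would mean is likely to look there. There is also a practical consequence. The final analysis will use Clopper-Pearson, so if an event occurs in exactly 1 or 30 of 675 subjects, the study report will print an interval that disagrees with the protocol's own table.

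**Working it through.** **Inputs.** n = 675 per group, two-sided 95% exact (Protocol section 10.1 and the title of Table 10); Clopper-Pearson (SAP 10.1.5.1); one decimal (SAP 10.1.4.1). No outside assumption is needed.

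**Formulas.** For x events in n subjects:

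- lower limit = 2.5% quantile of Beta(x, n − x + 1), taken as 0 when x = 0
- upper limit = 97.5% quantile of Beta(x + 1, n − x)

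**The whole table recomputed.**

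| Events | Observed % | Lower, computed | Lower, printed | Upper, computed | Upper, printed | Agree at 1 decimal? |
|---|---|---|---|---|---|---|
| 0 | 0.0 | 0 | 0.0 | 0.545 | 0.5 | yes |
| 1 | 0.148 | 0.004 | 0.0 | 0.823 | 0.7 | **upper: no (0.8)** |
| 10 | 1.481 | 0.713 | 0.7 | 2.708 | 2.7 | yes |
| 30 | 4.444 | 3.018 | 3.0 | 6.284 | 6.2 | **upper: no (6.3)** |
| 50 | 7.407 | 5.548 | 5.5 | 9.649 | 9.6 | yes |
| 100 | 14.815 | 12.219 | 12.2 | 17.722 | 17.7 | yes |

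Ten of the 12 limits reproduce, and all six observed percentages are right.

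**Direct check of the one-event row.** The upper limit is the rate p at which seeing one event or fewer has probability 0.025:

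P(X ≤ 1) = (1 − p)^675 + 675 p (1 − p)^674

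- At p = 0.8226%: 0.0038 + 0.0212 = 0.0250, as required.
- At p = 0.70%: 0.0087 + 0.0415 = 0.050, twice the permitted tail.
- At p = 0.75%, the top of the range that displays as 0.7%: 0.038, still too large.

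**Direct check of the 30-event row.** P(X ≤ 30) is 0.0250 at p = 6.284%, 0.030 at 6.20% and 0.027 at 6.25%.

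So no value that displays as 0.7% or 6.2% is a valid 95% exact upper limit for these rows.

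**Could another convention explain the printed figures?** None tried gives the whole table.

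- Truncating instead of rounding gives 6.2% but leaves the one-event limit at 0.8%. The table also rounds elsewhere: 1.48% is shown as 1.5%.
- A two-sided 90% interval gives 0.701% for one event but 5.98% for 30.
- Mid-P gives 0.73% and 6.2% but 0.44% for zero events (printed 0.5%) and 2.6% for 10 (printed 2.7%).
- Blaker's exact interval gives 6.24% for 30 events but 0.82% for one.
- Wilson, Agresti-Coull, Jeffreys, Wald, a Sterne-type exact interval and exact Poisson also fail.
- A different n does not help: 0.7% for one event needs n between 741 and 854, and 6.2% for 30 events needs n between 679 and 689. The ranges do not overlap.

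**Size in plain terms.** 1/0.008226 is about 122; 1/0.007 is about 143. At n = 741 the one-event limit is 0.7496%, the first to round to 0.7%; at n = 794 it is 0.6997%, the first below 0.70%. These sample sizes only show the scale of the discrepancy; they are not a proposal to enlarge the trial.

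**The case against.** The strongest reply is that nothing depends on these cells. No threshold, margin or stopping boundary refers to 0.7% or 6.2%, no interim analysis is planned, and every reported interval will be computed afresh from the observed data. Section 10.1 does not say that 675 was derived from Table 10; the stated reason for the size is the safety database agreed with the regulator. On this view the finding is an erratum of 0.1 point in an illustrative table.

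Much of that stands. The sample size and analyses are unaffected, and the database rationale is a genuine second reason for the size. It has no figures, however, so Table 10 remains the only quantitative statement of what the sample size achieves.

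Three narrower points also stand:

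- Only the one-event row concerns a rare event. The 30-event row is a 4.4% rate, and the zero-event bound, which also serves rare events, is correct.
- The 1 in 143 comparison reads 0.7% as exactly 0.700%. At the edge of rounding, 0.75%, it would be about 1 in 133.
- The match between 0.7% and a 90% interval fits one cell only and does not establish how the error arose.

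None of this makes the printed limits right, and nothing elsewhere in the protocol or SAP corrects them.

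**Conclusion.** The concern holds. Under the method, confidence level, sample size and display rule that the documents set, the upper limit is 0.8% (0.823%) for 1/675 and 6.3% (6.284%) for 30/675. Table 10 understates both, by 0.1 percentage point each as displayed. Measured from the unrounded limit, the one-event shortfall is 0.12 point if 0.7% is read as exactly 0.700%, and at least 0.07 point if it is read as anything up to 0.75%.

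Both errors favour the design, and they sit in the only numerical support the protocol gives for its sample size, so they should be corrected. The effect is confined to the stated precision; the choice of 675 per group and the planned analyses are untouched. The result rests on the Clopper-Pearson method named in the SAP being the one meant by exact in the title of Table 10.

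**What to change.** In Protocol Table 10, change the upper limit for 1 event from 0.7% to 0.8%, so the row reads 0.0% to 0.8%, and the upper limit for 30 events from 6.2% to 6.3%, so the row reads 3.0% to 6.3%. It would help to name Clopper-Pearson in the table title or a footnote, in line with SAP 10.1.5.1.

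The cost is two table cells and a slightly less favourable statement of precision.

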10.2. Populations for analyses

For purposes of analysis, the following analysis sets are defined:

Analysis set	Description
Enrolled	All subjects who were randomized or vaccinated
Exposed	All subjects who received at least 1 dose of the study treatment. For the sake of analysis, the study group is defined by the treatment administered at Dose 1.

10.3. Statistical analyses

10.3.1. Subjects disposition

Number of enrolled, vaccinated (at least 1 vaccination, full vaccination course) subjects and reason for withdrawal, included in each study group or in total will be described.

10.3.2. Demography and baseline characteristics analyses

The median, mean, range and standard deviation of age (in weeks) at each study vaccine dose and of the gestational age at birth will be computed by study group. The median, mean and standard deviation of length (in centimeters) and weight (in kilograms) at Visit 1 will be computed by study group. The distribution of racial and sex composition of the study population will be presented.

The distribution of subjects enrolled in each country/site will be tabulated across and per study group.

CONFIDENTIAL208236 (ROTA-096)
Protocol Amendment 2

Important protocol deviations including ineligibility, unblinding, mis-administration of treatment, use of prohibited medication/vaccination and deviations from intervals between vaccination Visit 1 and Visit 2 (see [Table 2](#)) will be tabulated by study group.

10.3.3. Safety analyses

The primary safety analysis will be performed on the Exposed set.

Endpoint	Statistical analysis methods
Primary	
Within groups assessment
 
The percentage of doses and of subjects reporting at least 1 AE (solicited or unsolicited) during the 8-day (Day 1-Day 8) solicited follow-up period post-vaccination will be computed, along with exact 95% CI. The same calculations will be done for AEs (solicited or unsolicited) rated as grade 3 in intensity, those assessed as causally related to vaccination, those rated as grade 3 in intensity with causal relationship to vaccination and those that resulted in a medically attended visit.
 
The percentage of doses and of subjects reporting each individual solicited general AE will be computed, over the 8-day (Day 1-Day 8) solicited follow-up period post-vaccination, along with exact 95% CI. The same calculations will be done for each individual general solicited AE rated as grade 3 in intensity, those assessed as causally related to vaccination, those rated as grade 3 in intensity with causal relationship to vaccination and those that resulted in a medically attended visit. For fever, additional analyses will be performed by 0.5°C increments. These calculations will also be performed by country, sex and frequent race.
 
The verbatim reports of unsolicited AEs will be reviewed by a physician and the signs and symptoms will be coded according to MedDRA. Every verbatim term will be matched with the appropriate preferred term. The percentage of subjects with unsolicited AEs occurring within 31-day (Day 1-Day 31) follow-up period after any dose with its exact 95% CI will be tabulated by group, and by preferred term. Similar tabulation will be done for unsolicited AEs rated as grade 3, for unsolicited AEs with causal relationship to vaccination, for unsolicited AEs rated as grade 3 with causal relationship to vaccination and those that resulted in a medically attended visit. These calculations will also be performed by country.
 
For each study group, the percentage of subjects who started taking at least 1 concomitant medication, antipyretic medication and prophylactic antipyretic medication during the 8-day (Day 1-Day 8) and 31-day (Day 1-Day 31) follow-up periods post-vaccination will be tabulated by dose, by subject for each dose and across the 2 doses.
 
Subjects who experienced at least 1 SAE during the entire study period (from Dose 1 till ESFU contact at Month 7-8) will be summarized by study group and all SAEs will be tabulated.

